3.2 OVERALL SCHEDULE OF TIMES AND EVENTS

Study Procedures	Screening Phase ^a	Baseline ^a	Combined Screening & Baseline Visit ^a			Tre	atment Phas	se	
Study Week				Week 4 ^b	Week 8 ^b	Week 12 ^b	Week 15 ^{b,s} (Trough 6MWD)	Week 16 ^b (at least 24 hours after Week 15)	Premature Discontinuation of Study Drug / Early Study Termination ^{s,t}
Study Day	-30 to -1	1	1	29	57	85	106	113	
Informed Consent	X		X						
Subject Eligibility ^c	X	X	X						
Pre-Baseline Review Form ^c	X		X						
Medical History with PH History and Demographics	X		X						
SGRQ		X	X					X	X
Physical Examination	X		X					X	X
Vital Signs ^d	X	X	X	X	X	X	X	X	X
Clinical Laboratory Assessments	X	X	X		X			X	X
NT-proBNP ^e		X	X		X			X	X
Blood Sample for Biomarker Evaluation (Optional) ^f		X	X					X	X
Blood Sample for Whole Genome Sequencing (Optional) ^g		X	X						
Urine Pregnancy Testh	X	X	X	X	X	X	X	X	X

Study Procedures	Screening Phase ^a	Baseline ^a	Combined Screening & Baseline Visit ^a			Tre	atment Phas	se	
Study Week				Week 4 ^b	Week 8 ^b	Week 12 ^b	Week 15 ^{b,s} (Trough 6MWD)	Week 16 ^b (at least 24 hours after Week 15)	Premature Discontinuation of Study Drug / Early Study Termination ^{s,t}
12-Lead ECG		X	X					X	X
6MWT ⁱ	X	X	X	X	X	X		X	X
Trough 6MWT ^j							X		
Pulse Oximetryk	X	X	X	X	X	X	X	X	X
Documentation of Supplemental Oxygen Requirement	X	X	X	X	X	X	X	X	X
PFTs ¹		X	X		X			X	X
Randomization		X	X						
Device Training		X	X						
Dosing instructions / Dosing / Dosing Diary / Accountability		X ^r	X ^r	X	X	X	X	X	X
Weekly Telephone / Email Contact ^m		X	X	X	X	X	X	X	
Adverse Events ⁿ	X	X	X	X	X	X	X	X	X
Concomitant Medications	X	X	X	X	X	X	X	X	X
Hospitalization due to a cardiopulmonary indication ^o	X	X	X	X	X	X	X	X	X
Exacerbations of Underlying Lung Disease ^p	X	X	X	X	X	X	X	X	X

Study Procedures	Screening Phase ^a	l	Combined Screening & Baseline Visit ^a			Tre	atment Phas	se	
Study Week				Week 4b	Week 8 ^b	Week 12 ^b	Week 15 ^{b,s} (Trough 6MWD)	l .	Premature Discontinuation of Study Drug / Early Study Termination ^{s,t}
Time to Clinical Worsening ^q		X	X	X	X	X	X	X	X

Abbreviations: ECG, electrocardiogram; NT-proBNP, N-terminal pro-brain natriuretic peptide; PFTs, pulmonary function tests; PH, pulmonary hypertension; SGRQ, St. George's Respiratory Questionnaire; 6MWT, 6-minute walk test; 6MWD, 6-minute walk distance; CT, computed topography; SpO₂, saturation of peripheral capillary oxygenation; HR, heart rate; eCRF, electronic case report form; FEV1, forced expiratory volume in 1 second; FVC, forced vital capacity; TLC, total lung capacity; DLCO, lung diffusion capacity; AE, adverse event; SAE, serious adverse event; 6MWD, 6-minute walk distance; ET, early termination

- ^a Screening Visit assessments can occur up to 30 days prior to the first dose of study drug. Baseline assessments can occur up to 48 hours prior to the first dose of study drug to allow for scheduling of all activities; however, the Baseline 6MWT must be performed prior to randomization. Screening and Baseline assessments may be combined if all entry criteria are satisfied within 48 hours prior to the first dose of study drug. Baseline PFTs, 6MWT, and CT scan (if a historical scan within 6 months is not available) assessments used to determine eligibility criteria must be performed prior to randomization. Sites should provide a completed Pre-Baseline review form to the Medical Monitor which will be reviewed, signed, and returned to the site prior to randomization.
- b The visit window for Week 4, Week 8, Week 12, Week 15, and Week 16 is ± 5 days. The Week 16 visit must occur at least 24 hours after the Week 15 visit.
- c For the Screening and Baseline Visits, the subject must be evaluated for and meet all inclusion/exclusion criteria.
- d Vital signs must be collected after 5 minutes of rest (seated); no other measurements or procedures should be performed during this 5-minute period. When possible, vital signs should be collected prior to the 6MWT. If vital signs cannot be obtained prior to the 6MWT then they should be obtained after recovery from the 6MWT.
- ^e Blood for NT-proBNP assessment must be drawn prior to conducting the 6MWT and will occur prior to randomization at Baseline (or as part of the Screening Visit assessment if the Screening and Baseline Visits are combined).
- f For subjects consenting to the optional biomarker sample.
- g For subjects consenting to the optional whole genome sequencing sample.
- h For females of childbearing potential.
- i If the subject has not previously undergone a 6MWT at the study site on the course intended for use during the study, a practice test must be conducted at the Screening Visit and must precede the Baseline 6MWT by at least 1 day. The Baseline 6MWT must precede randomization. The Week 4, Week 8, Week 12, and Week 16 peak 6MWT must occur within 10 to 60 minutes after the most recent study drug dose. Prior to the start of each 6MWT the subject should rest (seated) for at least 10 minutes. Subjects receiving supplemental oxygen during the Baseline 6MWT must continue to receive the same flow rate at all subsequent 6MWT assessments. The supplemental oxygen flow rate must be recorded at each study visit, as applicable.
- The Week 15 trough 6MWT must occur at least 4 hours after the most recent study drug dose and at least 24 hours prior to the Week 16 6MWT. Subjects receiving supplemental oxygen during the Baseline 6MWT must continue to receive the same flow rate at all subsequent 6MWT assessments. The supplemental oxygen flow rate must be recorded at each study visit, as applicable.

- ^k Pulse oximetry will be performed immediately prior to, during, and immediately following each 6MWT. Pulse oximetry will include the measurement of SpO₂ and HR. The SpO₂ and HR obtained immediately prior to and immediately following completion of the 6MWT will be recorded in the eCRF. In addition, the lowest recorded SpO₂ obtained during each 6MWT will be recorded in the eCRF.
- ¹ PFTs will include the evaluation of FEV1, FVC, TLC, and DLCO. Baseline PFTs must be performed prior to randomization. PFTs should be performed after recovering from the Baseline, Week 8, and Week 16 or ET 6MWTs.
- ^m At least weekly telephone contact is required throughout the study (may be replaced by a face-to-face interaction on the weeks where study visits occur and the information can be obtained during the visit). Subjects may be contacted via email in lieu of a telephone call. A copy of the emails and/or telephone contact sheets must be documented in the subject's source documentation. Email should not replace direct follow-up by phone or in clinic for clinically significant AEs or other emergent issues.
- All AEs will be documented from the time of informed consent until the time screen failure is documented, or until the subject is either discontinued from the study or all Week 16 study assessments have been completed and should be followed until either resolution (or return to normal or base line values), until they are judged by the Investigator to no longer be clinically significant, or for at least 30 days if the AE extends beyond the final study visit (Week 16).
- On Hospitalizations due to cardiopulmonary indications must be recorded in the eCRF from the time of informed consent until study termination. Adverse events resulting in hospitalizations, regardless of cause or duration, should also be recorded as SAEs per Appendix 15.2.
- P Exacerbations of underlying lung disease; defined as an acute, clinically significant, respiratory deterioration characterized by evidence of new widespread alveolar abnormality (see Section 3.3.2.10). Exacerbations will also be recorded as AEs or SAEs per Appendix 15.2.
- ^q Time to clinical worsening will be measured from the time of randomization until 1 of the following criteria are met: hospitalization due to a cardiopulmonary indication; decrease in 6MWD > 15% from Baseline directly related to the disease under study, at 2 consecutive visits and at least 24 hours apart; death (all causes); or lung transplantation.
- ^r Once all entry criteria have been met and the randomized treatment assignment confirmed, the first dose of study drug (3 breaths; 18 mcg) will be inhaled in the clinic, followed by at least a 1 hour observation period (Defined as Day 1).
- Subjects who permanently discontinue study drug during the 16-week Treatment Phase are encouraged to undergo premature termination assessments prior to discontinuing study drug and are required complete all remaining scheduled study visits through Week 16 (excluding the Week 15 Visit) to be eligible for entry into the open-label study.
- ^t The premature termination of study drug visit should be conducted prior to study drug discontinuation or as close as possible to the last dose of study drug.

3.3 CLINICAL ASSESSMENTS

3.3.1 Efficacy

3.3.1.1 6-Minute Walk Test

The 6MWT is a validated and reliable measure of exercise capacity in patients with chronic respiratory diseases (Holland 2014). This study will utilize an unencouraged 6MWT to minimize potential bias associated with encouragement. All 6MWTs will be conducted by qualified, trained personnel in a designated 6MWT area which meets the requirements as described in Appendix 15.1. Prior to the start of each 6MWT the subject must rest (seated) for at least 10 minutes. This 6MWT protocol applies to the practice (if applicable), Baseline, and treatment 6MWTs. Subjects receiving supplemental oxygen during the Baseline 6MWT must continue to receive the same flow rate at all subsequent 6MWT assessments. Pulmonary rehabilitation may not be introduced to a subject's treatment regimen between randomization and Week 16 or until the permanent discontinuation of study drug. Pulse oximetry is to be performed immediately prior to, during, and immediately following each scheduled 6MWT as outlined in Section 3.3.2.6.1.

3.3.1.1.1 Practice 6-Minute Walk Test

All subjects must have a documented 6MWT conducted at the study site on the course intended for use during the study. Subjects who have not previously performed the 6MWT at the study site on the course intended for use during the study, must perform a practice 6MWT at the study site at least 1 day prior to the Baseline Visit.

3.3.1.1.2 Baseline 6-Minute Walk Test

The Baseline 6MWT must be performed prior to randomization. Pulse oximetry is to be performed immediately prior to, during, and immediately following each scheduled 6MWT as outlined in Section 3.3.2.6.1.

Note: The Baseline 6MWT (not the practice 6MWT) will determine the subject's eligibility to participate in the study $(6MWD \ge 100 \text{ meters per inclusion criteria})$.

3.3.1.1.3 Treatment 6-Minute Walk Tests

3.3.1.1.3.1 Peak 6-Minute Walk Tests

Peak 6MWTs will be conducted at Weeks 4, 8, 12, and 16 or Early Termination (ET). The 6MWT must be conducted between 10 to 60 minutes after the most recent dose of study drug. If subjects are receiving supplemental oxygen during the Baseline 6MWT, they must continue to receive the same flow rate at all subsequent 6MWT assessments. The Week 16 peak 6MWT should occur at least 24 hours after the Week 15 Visit. Refer to Appendix 15.1 for guidelines regarding the 6MWT assessment. Pulse oximetry is to be performed immediately prior to, during, and immediately following each scheduled 6MWT as outlined in Section 3.3.2.6.1.

3.3.1.1.3.2 Trough 6-Minute Walk Test

A trough 6MWT will be performed during the Week 15 Visit. The trough 6MWT must be performed at least 4 hours after the most recent dose of study drug and at least 24 hours prior to the Week 16 6MWT. If subjects are receiving supplemental oxygen during the Baseline 6MWT, they must continue to receive the same flow rate at all subsequent 6MWT assessments. Refer to Appendix 15.1 for guidelines regarding the 6MWT assessment. Pulse oximetry is to be performed immediately prior to, during, and immediately following each scheduled 6MWT as outlined in Section 3.3.2.6.1.

Subjects who discontinue study drug prematurely prior to the Week 15 Visit do not need to return to the clinic for the Week 15 Visit to be eligible for participation in the open-label extension study (Section 7.8).

3.3.1.2 St. George's Respiratory Questionnaire

The SGRQ will be conducted at Baseline (prior to study drug) or as part of the Screening Visit assessment if the Screening and Baseline Visits are combined and at Week 16 (or ET for those subjects discontinuing study drug/study prematurely). The SGRQ should be completed as the first assessment during these visits (after informed consent is obtained) before the subject completes any of the other scheduled visit assessments. A copy of the SGRQ can be found in Appendix 15.3.

3.3.1.3 N-terminal Pro-brain Natriuretic Peptide

Plasma NT-proBNP concentration is a useful biomarker associated with changes in right heart morphology and function (Fijalkowska 2006). NT-proBNP sample collection will occur at Baseline (or as part of the Screening Visit assessment if the Screening and Baseline Visits are combined) prior to starting study drug, Week 8, and Week 16 or ET. Blood for NT-proBNP assessment must be drawn prior to conducting the 6MWT.

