3.3.2.5 Pulmonary Function Tests

Pulmonary Function Tests will be assessed at Baseline and repeated at Week 8 and Week 16 or ET. Baseline PFTs are to be conducted prior to randomization and after recovery from the 6MWT. The Week 8 and Week 16 or ET PFTs should be conducted after recovery from the 6MWT. If the PFTs are done both prior to and after a bronchodilator, only the prebronchodilator values will be recorded.

The following parameters will be recorded (absolute values and % predicted): FEV1, FVC, TLC, and DLCO (uncorrected for hemoglobin and lung volume).

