# 5 SAMPLE SIZE CONSIDERATIONS

Using an allocation ratio of 1:1 between inhaled treprostinil and placebo, a sample size of approximately 266 subjects (133 per treatment) would provide at least 90% power at a significance level of 0.05 (2-sided hypothesis) to detect a 30 meter between-treatment difference in the change from Baseline to Week 16 in 6MWD, assuming a standard deviation of 75 meters.

The total sample size will be approximately 314 subjects to account for a discontinuation rate of approximately 15%.

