# 8.1 COVARIATES

The primary efficacy analyses of change in 6MWD at Week 16 will be adjusted for Baseline 6MWD (as a continuous variable). For sensitivity analyses of the primary efficacy endpoints and the secondary/exploratory endpoints with continuous variables, the baseline measure will always be the covariate.

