### 8.2 EXAMINATION OF SUBGROUPS

For primary efficacy endpoints of change in 6MWD at Week 16, subgroup analyses will be performed. These subgroups will include:

- Etiology of ILD (Idiopathic Interstitial Pneumonia [IIP], Chronic Hypersensitivity Pneumonitis [CHP], Occupational, CPFE, Connective Tissue Disease [CTD], and Other)
- Baseline walk categories (≤350 meters versus >350 meters, ≤ median baseline 6MWD versus > median baseline 6MWD)
- ILD disease severity as measured by Baseline DLCO (<40% predicted versus ≥40% predicted)

- Sex (male versus female)
- Pulmonary Vascular Resistance (PVR) (<4 versus ≥4 Wood Units [WU])
- Age group (<65 years of age, 65 to <80 years of age, and  $\geq$ 80 years of age)
- Study drug dose at Week 16 (0 to 3 breaths, 4 to 6 breaths, 7 to 9 breaths, and 10 to 12 breaths)

No Type 1 error adjustments will be performed for these subgroup analyses.

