# 10.1.1.2 Primary Efficacy Analysis

All 6MWT data will be listed for all subjects. For each scheduled assessment, this listing will include the date test was performed (or date test was intended to be performed if subject is unable to attempt the test), start time of the test, nominal time point, last treatment dose, hours from last treatment dose to 6MWT start, if walk was attempted, total distance walked (in meters), whether subject received oxygen during the test, amount of supplemental oxygen, and any circumstances that adversely affected the walk (if any) including reason for not

attempting test (if any). The trough 6MWT measure will also be indicated. In addition, a listing of 6MWD with imputed values will be included for both peak and trough 6MWD data.

For the primary efficacy analysis, the effect of inhaled treprostinil versus placebo on change in peak 6MWD at Week 16 will be evaluated via analysis of covariance (ANCOVA). Change from Baseline in peak 6MWD is the dependent variable, and treatment and Baseline 6MWD are covariates in this ANCOVA model. Least squares means and standard errors for each treatment group, the least squares mean difference and its standard error, as well as a 95% confidence interval for the treatment group difference and p-value for treatment group comparison will be calculated from the ANCOVA model. This methodology will be carried out as follows:

- 1. Walk distances obtained after study drug termination or unblinding will be excluded (as described in Section 8).
- 2. Imputation rules in Table 8-1 will be applied.
- 3. The LOCF algorithm will be applied.
- ANCOVA will be conducted based on the pseudo SAS code: proc glm; class Treatment; model DistC = Treatment Dist0; run;

where DistC is the change from Baseline in peak 6MWD at Week 16 and Dist0 is the baseline measure of the 6MWD.

If the ANCOVA assumptions are violated, the primary efficacy analysis will be based on non-parametric analysis of covariance within the framework of the extended Cochran-Mantel-Haenszel test (Koch 1990, Koch 1998, Stokes 2000). Specifically, a Cochran-Mantel-Haenszel mean score test will be used on the standardized mid-ranks (ie, overall rank divided by the number of ranks +1, or "modified ridit" scores) of the residuals from an ordinary least squares regression with change from Baseline in peak 6MWD at Week 16 as a linear function of distance walked at Baseline (as a continuous variable). This methodology will be carried out as follows:

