In addition, the impact of Baseline hemodynamics and Baseline PFTs, including PVR, PAPm, PCWP, FEV1, FVC, TLC, and DLCO as continuous variables, on peak 6MWD, will be explored using the regression approach.

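### Free improvement, not an error: the 6MWD models adjust only for Baseline 6MWD, although Baseline NT-proBNP and DLCO are scheduled before randomisation and could be added at almost no cost

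*Protocol*

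**What the plan says.** **What is measured, and when.** Protocol 3.3.1.3 introduces NT-proBNP with the statement that "Plasma NT-proBNP concentration is a useful biomarker associated with changes in right heart morphology and function". The notes to the schedule in Protocol 3.2 place the baseline draw before randomisation. Protocol 3.3.2.5 says that "Baseline PFTs are to be conducted prior to randomization", and the PFTs include DLCO, recorded in absolute and % predicted form. Unlike the biomarker and genome samples, neither measurement is optional.

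**What the primary model contains.** SAP 10.1.1.2 states that "treatment and Baseline 6MWD are covariates in this ANCOVA model", and its code has the two terms Treatment and Dist0. SAP 8.1 names the same single baseline covariate. The rank-based fallback in 10.1.1.2 regresses on Baseline 6MWD alone. SAP 10.2.1 (Week 12 peak) and 10.2.3 (Week 15 trough) reuse the method of 10.1.1.2.

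**Where the two markers appear instead.** DLCO appears in three places:
- as a subgroup factor in SAP 8.2, described as "ILD disease severity as measured by Baseline DLCO";
- in a stratified sensitivity analysis in SAP 10.1.1.3, planned only if the primary result is significant;
- in an exploratory analysis in the same section, where baseline haemodynamics and PFTs "as continuous variables, on peak 6MWD, will be explored using the regression approach".

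Baseline NT-proBNP appears in none of these. It is a covariate only in the analysis of NT-proBNP itself (SAP 10.2.2).

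**The concern.** A pre-randomisation variable that predicts the outcome, beyond the covariates already in the model, reduces residual variance when it is added. The comparison stays unbiased in expectation and the Type 1 error is unaffected, provided the model is fixed in advance. The plan collects two candidates and describes both as disease-relevant, but leaves them out of the model that tests the treatment.

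Three of the four tests in the fixed sequence of SAP 8.4 are walk tests using this model, and every later test depends on the primary. The other uses of DLCO do not serve the same purpose. The stratified analysis runs only after a significant primary result, so it cannot sharpen a borderline one. The exploratory regression is a separate analysis and does not replace the primary test.

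Table 8-1 gives one reason to expect some prognostic value. A walk missing because of death, clinical worsening or being too ill is scored 0 m, which is a very large fall. Markers of right heart function and ILD severity are natural candidates for predicting who falls into that group. That is a plausible expectation, not something the documents show.

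**Working it through.** **Inputs from SAP 5:** difference 30 m; SD 75 m; two-sided alpha 0.05; power at least 90%; 133 per arm (266); about 15% discontinuation; about 314 randomised.

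**Step 1. Reproduce the plan.** For a two-sample t-test, SE = SD × √(2/n) = 75 × √(2/133) = 9.20 m. The noncentrality is 30/9.20 = 3.26, and the noncentral t gives power 90.1%. The smallest n reaching 90% is 133 per arm, so 266 is reproduced exactly. The normal approximation gives 132 per arm. Inflating for discontinuation, 266/0.85 = 313, against the stated 314.

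**Step 2. Add the covariates.** Let R² be the share of the remaining variance explained jointly by Baseline NT-proBNP and DLCO after Baseline 6MWD. The documents give no value, so a range is assumed. The residual SD is 75 × √(1 − R²). The equivalent gain in subjects is 266/(1 − R²) − 266.

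| Assumed R² | Residual SD (m) | SE at 133 per arm (m) | Power | Equivalent extra subjects |
|---|---|---|---|---|
| 0% | 75.0 | 9.20 | 90.1% | 0 |
| 3% | 73.9 | 9.06 | 91.0% | 8 |
| 5% | 73.1 | 8.96 | 91.5% | 14 |
| 10% | 71.2 | 8.73 | 92.9% | 30 |

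**Step 3. Use the number likely to be analysed.** The ITT population in SAP 6 takes every dosed subject, and Table 8-1 imputes missing walks. About 314/2 = 157 per arm would therefore enter the model. Holding 30 m and SD 75 m, SE = 75 × √(2/157) = 8.46 m. Power is about 94.2%, 94.8%, 95.2% and 96.1% for R² of 0%, 3%, 5% and 10%.

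**Step 4. Cost if the markers are useless.** At 133 per arm, residual degrees of freedom fall from 266 − 3 = 263 to 261. The effect on power is negligible.

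**Step 5. Missing baseline values.** SAP 8.3.2 anticipates that some subjects lack Baseline NT-proBNP. If a share m were dropped from the model, the squared SE would be proportional to (1 − R²)/(1 − m), so the gain is cancelled when m = R². With 5% dropped and R² of 2%, power falls below the starting point: 89.5% against 90.4%, both by the normal approximation. The change is therefore safe only with a rule that keeps every ITT subject.

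**Limits.** These are normal-theory figures and do not cover the rank path. They treat 75 m as the residual SD after Baseline 6MWD, which SAP 5 does not state. The 0 m scores could change both the SD and R².

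**The case against.** The strongest reply is that nothing here is wrong. The model is prespecified, adjusts for the baseline of its own outcome (in categories, also the only stratification factor), and reaches its stated power. Adding two markers is a modelling preference. That stands, and it is why the point is offered as an improvement only.

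Four stronger readings are tempting, and the documents support none of them.

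- **Precision is definitely being lost.** No section links either marker to change in 6MWD after Baseline 6MWD. The NT-proBNP sentence concerns the right heart, not walking. Calling DLCO a measure of severity does not make it prognostic for a 16-week change. Any R² is an assumption, including a range simulated from assumed inputs.
- **The trial is short of power.** It has 90.1% at 133 per arm on its own inputs, and about 94% at 157. Whether 75 m allows for the 0 m scores is not stated. That is a separate sample-size question, and covariate adjustment would be only a partial answer to it.
- **DLCO is ignored.** It has the three other uses listed above.
- **Both values will exist in every subject.** They are scheduled for every subject, but SAP 8.3.2 foresees missing Baseline NT-proBNP. Filling gaps keeps subjects in the model but somewhat reduces the gain.

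It is also fair to note that DLCO is recorded without correction for haemoglobin or lung volume, across about 120 centres. The resulting noise would tend to lower its R².

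**Conclusion.** The point holds as a free improvement. Two baseline markers scheduled before randomisation are left out of the primary model, its fallback and the two secondary walk tests, and including them would be valid and cheap. The size is modest and conditional. For an assumed joint partial R² of 3% to 10%, the SE falls by about 1.5% to 5%, and power rises by roughly 1 to 3 points at 133 per arm or 0.6 to 2 points at 157. At an R² of zero there is essentially no gain and no harm. This rests on the planning values of 30 m and 75 m, normal-theory power, prespecification before unblinding, and no loss of ITT subjects.

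**What to change.** Before unblinding:

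1. In SAP 8.1 and 10.1.1.2, change the model to DistC = Treatment Dist0 logBNP0 DLCO0, where logBNP0 is log Baseline NT-proBNP and DLCO0 is continuous Baseline DLCO % predicted.
2. In the rank-based fallback, rank both markers and add them to the PROC REG step.
3. Fill a missing baseline covariate with the pooled mean over both arms, computed blind to treatment, so that no ITT subject leaves the model.
4. State that the same covariates apply to the Week 12 peak and Week 15 trough tests.
5. Keep the model with Baseline 6MWD alone as a prespecified supportive analysis.

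The cost is SAP wording, a few lines of code and two degrees of freedom. No new data, visits or subjects are needed.
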